6.4.1 Criteria for Discontinuation of Study Intervention

In addition to the drug-specific discontinuation criteria listed in section 7.2, the following will result in treatment discontinuation:

- Subject withdraws consent from the study treatment and/or study procedures. A subject must be removed from the trial at his/her own request. At any time during the trial and without giving reasons, a subject may decline to participate further. The subject will not suffer any disadvantage as a result.
- Any AE that requires a dose interruption > 28 days.
- Unacceptable AE or toxicity that cannot be managed by supportive care.
- Other AEs or intercurrent illnesses which, in the opinion of the investigator, would be injurious to the health or well-being of the subject and warrant their withdrawal from study treatment.
- Necessity for prohibited treatment (as defined in section 6.3) of sufficient dose and duration to confound the study results.
- Sexually active subjects who refuse to use medically accepted barrier methods of contraception (as defined in section 7.4) during the course of the study and for 3 months after discontinuation of study treatment.
- Women who become pregnant or are breastfeeding.
- Significant non-compliance with the protocol schedule or treatment in the opinion of the investigator.
- Subject is lost to follow-up or dead.
- Request by regulatory agencies for termination of treatment of an individual subject or all subjects under the protocol.

Any patient who does not withdraw from the study but who stops attending study visits and does not respond to 3 documented contact attempts will be considered lost to follow-up.

All patients will be followed until disease progression, withdrawal of consent, occurrence of any withdrawal criteria, loss of clinical benefit or intolerable toxicity precluding further treatment with study treatment, death or loss to follow up.

6.4.2 Criteria for Withdrawal from the Study

Subjects will be taken off study for the following:

- Completed study follow-up period
- Participant requests to be withdrawn from study
- Death

- Screen failure
- The study is discontinued at the discretion of the PI or drug manufacturer for any reason, including medical or ethical reasons affecting the continued performance of the study, or difficulties in the recruitment of patients

7 TOXICITIES AND DOSAGE MODIFICATION

This study will utilize the CTCAE (NCI Common Terminology Criteria for Adverse Events) Version 5.0 for adverse event and serious adverse event reporting.

While drug-related major organ toxicities are not prominent, selinexor treatment can lead to a number of constitutional and other side effects. Therefore, patients should be treated aggressively with supportive care to reduce toxicities and prevent the need for dose modifications.

Based on preliminary observations from the ongoing Phase 1 studies in patients with advanced hematological and solid tumors, selinexor shows a reasonably wide therapeutic range with activity observed at doses ranging from ~ 6 mg/m² to ≥ 60 mg/m² (approximately 10 mg to 120 mg orally).

Therefore, in order to optimize specific anti-tumor activity and tolerability, dose modifications and treatment delays will be allowed as described below. Each dose modification or treatment delay must be documented (including the reason for the modification or delay).

7.1 Dose Modifications

For patients enrolled after protocol version 7, alternate dosing schedules, dose reductions, and/or treatment delays in response to AEs are allowed as defined in Table 3 below.

Dose interruptions are due to non-resolving adverse events lasting > 28 days are prohibited and will result in permanent discontinuation from treatment.

Refer to Section 7.2 and Table 4 for dose reduction and interruption recommendations for specific AEs.

Table 3: Pre-specified Dose Modifications for AEs Related to Selinexor

	Dose Level	Dose of Selinexor
Dose Escalation	1	60 mg once weekly
Starting Dose	0	40 mg once weekly
Dose reduction	-1	20 mg once weekly

Dose escalation for selinexor is allowed after 12 weeks if no grade 2 or higher weight loss occurred. Dose escalation is at the discretion of the treating physician and requires documented consultation with the PI and medical monitor.

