6 TREATMENT PLAN

6.1 Administration Schedule

The schedule is based on 28-day cycles.

For patients enrolled after protocol version 7, Selinexor will be administered by oral route, beginning at 40 mg once weekly. Prior to protocol version 7, the starting dose of selinexor was 60 mg and 80 mg once weekly.

In case of toxicity at the starting dose level, dose modifications will be implemented as described in Section 7.1. Treating investigators may consider increasing the dose to 60 mg once weekly after 12 weeks of treatment in the absence of grade 2 or higher weight loss. The dose increase must be done after documented consultation with PI and medical monitor.

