Grade 2 weight loss Grade 3 anorexia, or Grade 3 weight loss	
Interrupt selinexor dosing until improved to Grade 1 or baseline and weight stabilizes. Reduce selinexor by 1 dose level.
 
Rule out other causes. Consider nutritional consultation and use nutritional supplements (e.g., Ensure®, Boost®)
 
Start appetite stimulants as above

Grade 4 anorexia	Permanently discontinue selinexor

Toxicity and Intensity	Supportive Care and Dose Adjustment Guidelines
Nausea, Acute	
Grade 1 or 2	Maintain dose. Rule out other causes. Use standard additional anti-nausea medications to supplement the protocol-required 5-HT3 antagonists. If persistent, use additional anti-nausea medications to supplement the protocol-required 5-HT3 antagonist(s). Olanzapine 2.5 to 5 mg PO every morning, per NCCN guidelines, can mitigate nausea and anorexia.
Grade 3	Rule out other causes. Use additional anti-nausea medications to supplement the protocol-required 5-HT3 antagonist(s). Olanzapine 2.5 to 5 mg PO every morning, per NCCN guidelines, can mitigate nausea and anorexia. Interrupt selinexor dosing until resolved to Grade ≤ 2 or baseline and reduce selinexor by 1 dose level. Patients with significant nausea/vomiting after several doses of selinexor may have an antitumor response. Consider an unscheduled assessment of tumor response as part of the patient's evaluation.
Hyponatremia	
Grade 1 (sodium levels < Normal to 130 mmol/L)	Maintain dose. Rule out other causes including drug (e.g., diuretic) effects. Be certain that reported sodium level is corrected for concurrent hyperglycemia (serum glucose > 150 mg/dL). Treat hyponatremia per institutional guidelines including dietary review. Provide supplemental oral and/or intravenous fluids if dehydration is present. Consider addition of salt tablets to patient's diet.
Grade 3 with sodium levels <130-120 mmol/L without symptoms	Rule out other causes including drug (e.g., diuretic) effects. Be certain that reported sodium level is corrected for concurrent hyperglycemia (serum glucose > 150 mg/dL). If (corrected) sodium is Grade ≤ 3 and continues to be asymptomatic, then patient may continue current dosing without interruption provided that IV saline and/or salt tablets are provided and patient is followed closely. If Grade 3 is persistent or worsens or does not respond to treatment, interrupt selinexor dosing until resolved to Grade 1 or baseline and reduce selinexor by 1 dose level.

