Grade 4	Permanently discontinue selinexor

^aFor all Grade ≥ 3 hematologic or Grade 3 non-hematologic AEs that are NOT selinexor related, after consultation with the principal Investigator, selinexor, dosing may be maintained.

^bFor all selinexor-related AEs, if the below prescribed dose reductions/interruptions result in a stabilization of ≥ 4 weeks, a re-escalation may be considered at the discretion of the treating physician, and consultation with the medical monitor if indicated, and requires authorization from the principal investigator.

All dose modifications should be based on the worst preceding toxicity.

^cFor all Grade 4 non-hematologic AEs that are NOT selinexor related, selinexor should be permanently discontinued.

Note: When toxicities due to selinexor have returned to baseline levels or the patient has stabilized, the dose of selinexor may be re-escalated at the discretion of the treating physician, and consultation with the medical monitor if indicated, and requires authorization from the principal investigator.

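### Table 4's two re-escalation notes give different waiting times, make medical monitor input optional, and do not fit the weight-loss condition for 60 mg in 6.1 and 7.1

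*Combined protocol and SAP*

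**What the plan says.** **Going up to 60 mg.** Section 6.1 gives the treating physician the option of "increasing the dose to 60 mg once weekly after 12 weeks of treatment in the absence of grade 2 or higher weight loss". Section 7.1 repeats the condition, "Dose escalation for selinexor is allowed after 12 weeks if no grade 2 or higher weight loss occurred", and adds that the step "requires documented consultation with the PI and medical monitor". Table 3 labels 60 mg the escalation level, 40 mg the starting dose and 20 mg the reduction level.

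**Coming down for weight loss.** For Grade 2 or 3 weight loss, Table 4 says: "Interrupt selinexor dosing until improved to Grade 1 or baseline and weight stabilizes. Reduce selinexor by 1 dose level". A patient on 60 mg therefore goes to 40 mg.

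**Going back up.** Footnote b to Table 4 covers all selinexor-related events: "if the below prescribed dose reductions/interruptions result in a stabilization of ≥ 4 weeks, a re-escalation may be considered". The Note that closes the table says: "When toxicities due to selinexor have returned to baseline levels or the patient has stabilized, the dose of selinexor may be re-escalated". On sign-off both use the same words: "consultation with the medical monitor if indicated, and requires authorization from the principal investigator".

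**Related text.** The confusion paragraph in 7.2 permits a cautious re-escalation once the patient is back to at least baseline, and names no waiting time or sign-off. Section 15.4 makes medical monitor approval a condition of every dose escalation. The lead-in to Table 3 is limited by enrolment date: "For patients enrolled after protocol version 7, alternate dosing schedules, dose reductions, and/or treatment delays in response to AEs are allowed". Table 4 carries no such limit.

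**The concern.** Weight loss is the one toxicity that 6.1 and 7.1 single out when deciding who may receive 60 mg. It is also the toxicity that 2.3.3 reports as the main reason for dose cuts before the starting dose was lowered to 40 mg. A patient who has Grade 2 or 3 weight loss while on 60 mg has shown that very toxicity at that dose. Following the Table 4 notes as written, that patient could be put back on 60 mg with no minimum wait and no required input from the medical monitor.

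Whichever rule is followed, the decision matches some sentence in the protocol, so no deviation would be recorded and similar patients could be handled differently. From cycle 7 the scheduled clinic visits, and the weights taken at them, may be three months apart unless the treating physician asks for more. The patient-level dose rules should therefore be clear.

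**Working it through.** No sample-size or error-rate figure is involved, so the check sets the rules side by side for one patient. The patient starts at 40 mg under version 7, completes 12 weeks without Grade 2 weight loss, is escalated to 60 mg after consultation, then has Grade 2 or 3 weight loss and is cut to 40 mg under Table 4. Weight then recovers. May the patient return to 60 mg?

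| Source | Wait before going back up | Weight-loss condition | Medical monitor | PI |
|---|---|---|---|---|
| 6.1 and 7.1 | 12 weeks of treatment (already served) | No Grade 2 or higher weight loss | Documented consultation | Documented consultation |
| Table 4, footnote b | At least 4 weeks of stability | None | Only if indicated | Authorization required |
| Table 4, closing Note | None stated | None | Only if indicated | Authorization required |
| 15.4 | Not addressed | Not addressed | Approval for all dose escalations | Not addressed |

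1. *Waiting time.* Footnote b and the Note sit together and cover the same events. One requires 4 weeks and the other accepts return to baseline, or stabilization, with no duration. This conflict does not depend on how 7.1 is read.
2. *Sign-off.* Three levels of medical monitor involvement apply to an upward dose step: optional (both notes), documented consultation (6.1 and 7.1), and approval (15.4).
3. *Weight loss.* Applied to this patient, the 7.1 condition is no longer met, because Grade 2 or higher weight loss has occurred. Both notes permit the return.
4. *Does 7.1 reach re-escalation?* An early sentence of 7.2 sends re-escalation to 7.1, whose only upward rule is the one above. That sentence concerns reductions for tolerable low-grade symptoms, so it supports reading 7.1 as governing but does not settle it.
5. *Earlier patients.* 2.3.3 reports four of the first 12 still on drug when version 7 was written, two on 60 mg and two on 40 mg. Because Table 3's lead-in covers only later enrolees, the text does not say whether 7.1 binds these four. If it does not, only the Table 4 notes apply to them, and the waiting-time conflict remains.

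*Background on the toxicity.* 2.3.3 reports Grade 2 weight loss in 5 of the 7 patients reduced to 40 mg, hence in at least 5 of 12 treated: 5/12 = 41.7%. The Clopper-Pearson 95% limits are the 2.5% point of Beta(5, 8) = 15.2% and the 97.5% point of Beta(6, 7) = 72.3%. All 12 started at 80 or 60 mg. The figure shows that the toxicity was common at those starting doses. It does not estimate how often the conflict would arise.

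**The case against.** The strongest reply is that escalation and re-escalation are different acts. On that reading, 6.1 and 7.1 control the first step above the starting dose, with the weight-loss condition as a one-time check on the first 12 weeks, and Table 4 controls the recovery of a dose already held. Nothing in 6.1 or 7.1 forbids re-escalation in terms. This much stands. A reader might infer that 6.1 and 7.1 prohibit the return to 60 mg outright. The documents do not support that, because the wording differs and the one cross-reference from 7.2 is limited to low-grade symptoms. The reading that 7.1 governs is still the better one: 60 mg is itself Table 3's escalation level, and it would be odd to hold recovery from mild symptoms to 7.1 while freeing recovery from Grade 2 or 3 weight loss.

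Safeguards exist. Both notes require PI authorization, so no treating physician can re-escalate alone, and Table 4 already requires improvement and a stable weight before dosing resumes. If re-escalation counts as escalation, 15.4 adds medical monitor approval, although its setting beside DLT and MTD notifications could suggest cohort steps. These limit the harm but do not tell the PI which rule applies.

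The Note's reference to a patient who has stabilized could be read together with footnote b's 4 weeks. Its other limb, return to baseline, still has no duration. For selinexor-related confusion, footnote b would supply the PI sign-off that the paragraph omits. The stopping rules withdrawn by 10.3.2 set cohort starting doses and never governed re-escalation, so their removal adds little.

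**Conclusion.** The point holds as an inconsistency in the dosing rules. Two elements rest on the text alone: the notes disagree on waiting time (at least 4 weeks against none), and their optional medical monitor role does not match 6.1, 7.1 or 15.4, to the extent that a return to 60 mg counts as an increase or escalation. The third, a return to 60 mg after Grade 2 or 3 weight loss, follows from the notes as written. It is at odds with the 6.1 and 7.1 condition without being expressly forbidden by it.

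The number of patients affected cannot be stated. A version 7 patient must first be escalated at discretion, then have the toxicity at 60 mg, then be proposed for 60 mg again, and the documents give a rate for none of these steps. A reader might infer from the 5 of 12 that about 40% of patients would meet the conflict. That is not supported: those patients started at 80 or 60 mg and the figure measures a different event. Nor can a count be inferred for the earlier patients still on treatment, since the text does not say whether 7.1 applies to them. The trial's sample size and primary test are unaffected. The correction should be made because it is cheap and concerns the toxicity behind the dose reductions.

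**What to change.** 1. Delete the Note under Table 4.
2. Amend footnote b along these lines: *After at least 4 weeks of stability, re-escalation may be considered with PI authorization and medical monitor approval (see 15.4). Any increase or return to 60 mg once weekly must also meet the condition in 7.1 that no Grade 2 or higher weight loss has occurred.*
3. In the confusion paragraph of 7.2, refer to footnote b.
4. State in 7.1 whether it applies to patients enrolled before version 7 who are still on treatment. The wording in item 2 restricts upward moves only, so it would not force down a patient already stable on 60 mg.

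If the sponsor does want to allow rechallenge at 60 mg after weight loss, the exception should be written into 6.1 and 7.1, with its own wait and sign-off.

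The cost is a few sentences of amendment, with no added visits or patients. The downside is that a few patients who might tolerate 60 mg again would stay at 40 mg, and those who recover quickly from other events would wait 4 weeks.

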7.2 Guidelines for Management of Adverse Events

Patients who are experiencing tolerable low-grade symptoms and are deriving clinical benefit from selinexor treatment may receive a dose reduction at the discretion of the enrolling

physician and after consultation with the PI (with subsequent re-escalation allowed as described in Section 7.1). Of note, the constitutional side effects associated with selinexor often attenuate over the first 4 to 6 weeks of treatment; nearly all are reversible with dose modification and/or supportive care.

Supportive care per institutional guidelines and/or National Comprehensive Cancer Network® Clinical Practice Guidelines in Oncology (NCCN) should be used as clinically indicated at the discretion of the treating physician.

Prophylactic therapy with 5-HT3 antagonists or other anti-nausea agents prior to each dose and as needed thereafter is required for all patients initiating selinexor treatment. Additional anti-nausea agents such as olanzapine, dopamine 2 antagonists, neurokinin 1 receptor antagonists, or others should be considered in any patients with insufficient response to initial therapy.

Particular attention should be also paid to anorexia with poor caloric intake which is often accompanied by poor fluid intake. This can lead to weight loss, dehydration, and fatigue. Nutritional consultation, frequent body weight assessments, and appetite stimulants (e.g., olanzapine or megestrol acetate) can mitigate anorexia and weight loss.

Some patients with rapid tumor responses experience significant fatigue, nausea, malaise and/or asthenia after 1 or more doses of selinexor. This effect has not been associated with typical markers of tumor lysis syndrome, but if suspected, assessment of tumor response is strongly recommended in order to better inform treatment recommendations.

Thrombocytopenia

Selinexor may induce reductions in platelet counts, with minimal effects on numbers of megakaryocytes. The effects of selinexor on platelet generation are related to a slowing of maturation of megakaryocytes and a reduction in their average ploidy. There is no known effect on platelet function, and bleeding associated with low platelets has been uncommon.

Interruption of selinexor therapy, when appropriate, may lead to return of platelet counts in 1 to 3 weeks. See Table 4 for specific guidance for managing Grades 1 through 4 thrombocytopenia. Thrombopoietin agonists, particularly romiplostim at moderate to high doses, have improved platelet counts in heavily pretreated patients receiving selinexor, permitting continued dosing and maintaining anti-neoplastic effects.

Neutropenia

Standard granulocyte growth factors are highly effective for the treatment of neutropenia observed during treatment with selinexor and should be used early in patients whose neutrophil counts decline during treatment. Patients should be instructed to report any symptoms or signs of infection such as fever, pain, sweating, and redness to their physician immediately. If infection during neutropenia is suspected, then standard treatment for febrile neutropenia may be instituted. Selinexor should be interrupted until the patient is clinically stable on appropriate antimicrobial agents. No known interactions with selinexor and antimicrobial agents have been reported, and selinexor may be restarted when the patient's condition has clinically stabilized.

Anemia

Selinexor-induced anemia may contribute to dizziness, confusion, syncope and/or fatigue, particularly in elderly patients and patients who are at greater risk of cognitive sequelae. As per NCCN Guidelines, treatment with red blood cell (RBC) transfusions and/or growth factors, per institutional guidelines, should be considered for patients with symptomatic anemia.

Nausea

In order to minimize nausea, all patients should receive 5-hydroxytryptamine (5-HT3) antagonists (8 mg or equivalent) unless contraindicated, starting on C1D1 before the first dose of study treatment and continued 2 to 3 times daily, as needed. Additionally, olanzapine (2.5 mg or higher) may be given prior to the first dose of selinexor and continued once daily (QD), up to 4 days, as per NCCN Guidelines. Patients with breakthrough nausea or vomiting should receive additional anti-emetic agents.

Infection

No prophylactic antimicrobial agent is recommended for most patients initiating therapy with selinexor. Patients with a history of recurrent infections or those at high risk for specific infections may continue their prophylactic antimicrobial regimens without modification when initiating selinexor therapy.

Selinexor should be withheld in patients with suspected or active uncontrolled infections, grade 4 infections, or clinical sepsis (in the absence of documented infection). Selinexor treatment can be resumed after initiation of appropriate antimicrobial therapy and when the infection has clinically resolved and/or the patient is clinically stable. When ready to resume selinexor, treatment may continue at the original dose, even in the setting of continued antimicrobial agents.

Diarrhea

Diarrhea associated with selinexor is typically watery and low-grade and usually responds to treatment with standard anti-diarrheal agents (e.g., loperamide) and/or dose modification. Careful assessment of the patient's volume status is essential. Fluid replacement is important to prevent dehydration, fatigue and electrolyte abnormalities (e.g., hyponatremia).

Fatigue

Prevention of anorexia, vomiting, and dehydration may reduce fatigue. Also, as per NCCN Guidelines, the use of methylphenidate 5 mg QD each morning may be helpful. Hemoglobin levels must be optimized as anemia appears to contribute substantially to fatigue, particularly in patients with heavily pretreated hematologic malignancies. In patients with adequate antitumor control on selinexor, QW dosing is often associated with improvement in fatigue and other side effects.

Decreased Appetite

In patients with problematic food/liquid/caloric intake secondary to anorexia, a patient log of food and drink, as well as body weights, should be considered and monitored by site staff. Nutritional counseling is important. Dysgeusia may contribute to the anorexia, and dietary

adjustments can be helpful. Fresh juices and simple carbohydrates, as well as ginger-containing foods and beverages, can improve appetite; ginger-containing foods may also improve dysgeusia. Administration of high caloric beverages (e.g., Boost®, Ensure®) and appetite stimulating agent(s) should be instituted aggressively in patients who develop significant anorexia.

A combination of appetite stimulating agents, particularly olanzapine (2.5 to 5.0 mg every morning), and standard anti-emetics is usually effective in managing selinexor associated anorexia that does not respond to the above interventions. Megesterol acetate 400 mg daily may also be effective. Additional information on the management of anorexia is provided in the NCCN Guidelines.

Hyponatremia

Investigators should rule out the possibility of pseudo-hyponatremia due to elevated glucose (or monoclonal protein) levels. Abnormal serum sodium levels should be corrected. Adequate fluid and caloric intake, including electrolyte-rich beverages instead of plain water, has led to reversal of hyponatremia. Diuretic use should be addressed and possibly stopped, and salt supplements should be considered if hyponatremia persists

Confusional State

Confusion is usually multifactorial with associated events including older age, dehydration, electrolyte abnormalities, anemia, diarrhea, infection, concomitant medications, other comorbidities and/or high tumor burden. Optimization of fluid status, electrolytes, hemoglobin levels, thyroid function, and concomitant medications should be undertaken. Glucocorticoids should be suspected and splitting the glucocorticoid dose over 2 days may be helpful. Other CNS-active agents should also be evaluated. However, confusion can be an isolated and dose-dependent event and thus a direct role for selinexor, which crosses the blood brain barrier, cannot be ruled out. Dose reduction of selinexor may be undertaken when other causes have been ruled out. If confusion resolves and patient returns to at least baseline status, cautious re-escalation of selinexor may be attempted.

Renal Insufficiency

Baseline renal insufficiency does not appear to affect tolerability of selinexor and renal dysfunction should not preclude continued dosing with selinexor, even for patients on dialysis. If a patient is undergoing dialysis, selinexor should be given after the dialysis procedure because the effect of dialysis on selinexor plasma levels has not yet been studied. Selinexor can lead to increased creatinine, and the majority of these cases are associated with hypovolemic conditions (i.e., represent “pre-renal” azotemia). Dose modifications or interruptions and appropriate hydration typically reverse the increased creatinine.

Vision Blurred and Cataracts

Patients reporting blurry vision or other visual changes should be evaluated by an ophthalmologist. Nearly all cases of treatment-emergent visual changes have not been associated with objective findings. Changes in lens prescriptions and/or wetting drops may improve vision. Blurred vision associated with selinexor use is typically self-limited, and dosing can usually be maintained at the same level and frequency.

Patients who are at risk of cataract formation, or have cataracts present at baseline, should be monitored for changes in lens opacity. If changes in lens opacity are observed, the patient should be evaluated by an ophthalmologist. In selinexor clinical studies, several patients have undergone cataract surgery with minimal to no interruption of selinexor dosing and without complications.

The relationship between cataract and selinexor is confounded by multiple contributing factors which are known risk factors for cataracts: the heavily pretreated nature of the patients' cancers, older age, pre-existing lens disease, and concomitant (and prior) medications including glucocorticoids.

The incidence and severity of occurrence of ocular AEs following treatment with selinexor was evaluated in a large, pooled-population of patients treated in all CSTs (N = 1458). These results show that new onset, clinically significant ophthalmological abnormalities following initiation of selinexor treatment were not commonly associated with objective findings upon ophthalmological examination

Tumor Lysis Syndrome

Tumor lysis syndrome (TLS) is rarely observed in patients treated with selinexor (see Section 5.5.2.3.1). It has been reported in 5 patients with MM, 2 patients with ALL, and 1 patient with AML. It has not been reported in any patient with NHL or solid tumor to date. All protocols require assessment of relevant screening laboratories and patient status (e.g., adequate hydration) to mitigate the risks for TLS.

Early recognition of signs and symptoms in patients at risk for TLS, including identification of abnormal clinical and laboratory values, is key and Investigators must ensure that patients being treated with selinexor maintain adequate caloric and fluid intake. Close monitoring and management of patients with hematological malignancies, including MM, for potential signs and symptoms of TLS are most relevant.

Based on the data received during the interval, evidence of a causal relationship between TLS and selinexor is not available at this point. Hence, it will remain as an important potential risk and Karyopharm will continue to monitor this event.

Overdose

As selinexor is metabolized by glutathione (GSH) conjugation, it is possible, but not demonstrated, that hepatic GSH depletion might occur in case of extreme overdose. Therefore, in patients who develop liver function test abnormalities, supportive measures such as S-adenosylmethionine (SAM) or other drugs that can replace GSH might be considered as part of the overall management plan.

Management guidelines for other selinexor-related AEs are provided in Table 4 below.

Table 4: Supportive Care and Selinexor Dose Adjustment Guidelines for AEs related to Selinexor^{a,b,c}

Toxicity and Intensity	Supportive Care and Dose Adjustment Guidelines
Fatigue	
Grade 1	
Maintain dose. Rule out other causes. If found to be anemic and symptomatic, consider transfusing even with hemoglobin >8 g/dL (anemia Grade <3).
 
Patients with significant fatigue after several doses of selinexor may have an antitumor response. Consider an unscheduled assessment of tumor response as part of the patient's evaluation.

Grade 2 lasting ≤7 days	
As per the NCCN guidelines, consider stimulants such as methylphenidate 5mg QD in the morning only.

Grade 2 lasting >7 days or Grade 3	
Rule out other causes. If found to be anemic and symptomatic, consider transfusions for hemoglobin >8 g/dL (Grade <3); transfusions usually indicated for Hb <8 g/dL (Grade ≥3). Interrupt selinexor dosing until resolved to Grade 1 or baseline.
 
For first occurrence, restart selinexor at current dose.
 
For ≥ second occurrence, reduce selinexor by 1 dose level.
 
Patients with significant fatigue after several doses of selinexor may have an antitumor response. Consider an unscheduled assessment of tumor response as part of the patient's evaluation.
 
As per the NCCN guidelines, consider stimulants such as methylphenidate 5mg QD in the morning only.

Anorexia or Weight loss	
Grade 1 anorexia	
Maintain dose. Rule out other causes. Consider nutritional consultation and use nutritional supplements (e.g., Ensure®, Boost®).
 
For persistent symptoms, start appetite stimulants, such as olanzapine (2.5 to 5 mg PO every morning) or megestrol acetate (400 mg QD), per NCCN guidelines.

Grade 1 weight loss Grade 2 anorexia	
Initiate appetite stimulants, such as olanzapine (2.5 to 5 mg PO every morning) or megestrol acetate (400 mg QD), as per NCCN guidelines.

Grade 2 weight loss Grade 3 anorexia, or Grade 3 weight loss	
Interrupt selinexor dosing until improved to Grade 1 or baseline and weight stabilizes. Reduce selinexor by 1 dose level.
 
Rule out other causes. Consider nutritional consultation and use nutritional supplements (e.g., Ensure®, Boost®)
 
Start appetite stimulants as above

Grade 4 anorexia	Permanently discontinue selinexor

Toxicity and Intensity	Supportive Care and Dose Adjustment Guidelines
Nausea, Acute	
Grade 1 or 2	Maintain dose. Rule out other causes. Use standard additional anti-nausea medications to supplement the protocol-required 5-HT3 antagonists. If persistent, use additional anti-nausea medications to supplement the protocol-required 5-HT3 antagonist(s). Olanzapine 2.5 to 5 mg PO every morning, per NCCN guidelines, can mitigate nausea and anorexia.
Grade 3	Rule out other causes. Use additional anti-nausea medications to supplement the protocol-required 5-HT3 antagonist(s). Olanzapine 2.5 to 5 mg PO every morning, per NCCN guidelines, can mitigate nausea and anorexia. Interrupt selinexor dosing until resolved to Grade ≤ 2 or baseline and reduce selinexor by 1 dose level. Patients with significant nausea/vomiting after several doses of selinexor may have an antitumor response. Consider an unscheduled assessment of tumor response as part of the patient's evaluation.
Hyponatremia	
Grade 1 (sodium levels < Normal to 130 mmol/L)	Maintain dose. Rule out other causes including drug (e.g., diuretic) effects. Be certain that reported sodium level is corrected for concurrent hyperglycemia (serum glucose > 150 mg/dL). Treat hyponatremia per institutional guidelines including dietary review. Provide supplemental oral and/or intravenous fluids if dehydration is present. Consider addition of salt tablets to patient's diet.
Grade 3 with sodium levels <130-120 mmol/L without symptoms	Rule out other causes including drug (e.g., diuretic) effects. Be certain that reported sodium level is corrected for concurrent hyperglycemia (serum glucose > 150 mg/dL). If (corrected) sodium is Grade ≤ 3 and continues to be asymptomatic, then patient may continue current dosing without interruption provided that IV saline and/or salt tablets are provided and patient is followed closely. If Grade 3 is persistent or worsens or does not respond to treatment, interrupt selinexor dosing until resolved to Grade 1 or baseline and reduce selinexor by 1 dose level.
Grade 3 with sodium levels <130-120 mmol/L with symptoms or Grade 4 (<120 mmol/L)	Rule out other causes including drug (e.g., diuretic) effects. Be certain that reported sodium level is corrected for concurrent hyperglycemia (serum glucose > 150 mg/dL). Interrupt selinexor dosing until resolved to Grade 1 or baseline and without symptoms. Reduce selinexor by 1 dose level.
Diarrhea	
Grade 1	Maintain dose. Rule out other causes including drug effects. Treat per institutional guidelines with anti-diarrheals, such as loperamide.
Grade 2	Rule out other causes including drug effects. Treat per institutional guidelines with anti-diarrheals. Interrupt selinexor dosing until resolved to Grade 1 or baseline. For first occurrence, restart selinexor at current dose. For \geq second occurrence, reduce selinexor by 1 dose level.
Grade 3	Interrupt selinexor dosing until resolved to Grade 1 or baseline and patient is clinically stable. Reduce selinexor dose by 1 dose level.
Grade 4	Permanently discontinue selinexor
Thrombocytopenia	
Grade 1 or 2	Maintain dose. Rule out other causes including drug effects.
Grade 3 without bleeding	Maintain dose. Rule out other causes including drug effects.

Toxicity and Intensity	Supportive Care and Dose Adjustment Guidelines
Grade 4 without bleeding	
Rule out other causes including drug effects. Platelet transfusion is allowed if clinically indicated at the discretion of the principal investigator.
 
For first occurrence: skip 1 dose and reduce selinexor by 1 dose level.
 
If recurrent, the investigator in consultation with the Medical Monitor may decide to continue selinexor dosing without dose reductions and/or interruptions as specified above, provided that platelet counts and bleeding symptoms/signs are closely monitored. Treatment with moderate to high doses of thrombopoietin stimulating agents such as romiplostim 5 to 10 µg/kg SC weekly or eltrombopag 100 to 150 mg QD can be considered at the discretion of the principal investigator. Platelet transfusion is allowed if clinically indicated at the discretion of the principal investigator.

Grade ≥ 3 with bleeding	
Interrupt selinexor dosing and check platelet counts weekly until the bleeding has stopped, patient is clinically stable and the platelets have recovered to Grade ≤ 3 or baseline. Platelet transfusion is allowed if clinically indicated at the discretion of the principal investigator. When resuming selinexor, reduce by 1 dose level.
 
If recurrent, unless contraindicated, start treatment with moderate to high doses of thrombopoietin stimulating agents as above.

Neutropenia	
Grade 4 neutropenia (afebrile) OR Febrile neutropenia	
Institute colony stimulating factors and prophylactic antibiotics as clinically indicated per institutional guidelines.
 
Interrupt selinexor and check neutrophils at least weekly until recovers to Grade 3 or baseline and without fever (if febrile) and the patient is clinically stable. Colony stimulating factors per institutional guidelines or at the discretion of the principal investigator. When resuming selinexor, reduce by 1 dose level.
 
If recurrent, continue colony stimulating factors, interrupt selinexor until neutrophil counts improve to Grade ≤ 3 or baseline levels. Investigator in consultation with the Medical Monitor may decide to continue selinexor dosing without dose reductions as specified above, provided that CBC and infection symptoms/signs are closely monitored.

Anemia	
Treat per institutional guidelines including blood transfusions and/or erythropoietins. Consider transfusing for symptoms with hemoglobin > 8 g/dL (Grade < 3) or for any Grade 3 (hemoglobin < 8 g/dL). If possible, maintain selinexor dose as long as patient is clinically stable, but if a dose reduction or interruption is desired, it should be done at the discretion of the treating physician and requires authorization from the principal investigator and consultation with the medical monitor if indicated.	
Other clinically significant selinexor-related adverse events	
Grade 1 or 2	Rule out other causes. Maintain dose. Start treatment and/or standard supportive care per institutional guidelines.
Grade 3	
Rule out other causes. Interrupt selinexor until recovers to Grade 2 or baseline and reduce selinexor by 1 dose level.
 
Isolated values of Grade 3 alkaline phosphatase do NOT require dose interruption. Determination of liver versus bone etiology should be made, and evaluation of gamma-glutamyl transferase, 5'-nucleotidase, or other liver enzymes should be performed.

Grade 4	Permanently discontinue selinexor

^aFor all Grade ≥ 3 hematologic or Grade 3 non-hematologic AEs that are NOT selinexor related, after consultation with the principal Investigator, selinexor, dosing may be maintained.

^bFor all selinexor-related AEs, if the below prescribed dose reductions/interruptions result in a stabilization of ≥ 4 weeks, a re-escalation may be considered at the discretion of the treating physician, and consultation with the medical monitor if indicated, and requires authorization from the principal investigator.

All dose modifications should be based on the worst preceding toxicity.

^cFor all Grade 4 non-hematologic AEs that are NOT selinexor related, selinexor should be permanently discontinued.

Note: When toxicities due to selinexor have returned to baseline levels or the patient has stabilized, the dose of selinexor may be re-escalated at the discretion of the treating physician, and consultation with the medical monitor if indicated, and requires authorization from the principal investigator.

